#### Secondary analyses

The analysis of each subgroup (males only and females only), will be analysed by one-way ANOVA, for summary statistics. Time-course data will be assessed by a two-way (time x treatment) repeated measures ANOVA. Paired t-tests will be used for post-hoc comparisons, which will be corrected for multiple comparisons using the Holm-Bonferonni adjustment.

To assess sex-by-treatment interaction effects, summary statistics will be analysed by a two-way (sex x treatment) mixed-model ANOVA. Time-course data will be analysed by three-way (sex x treatment x time) mixed-model ANOVA. Unpaired t-tests will be used for post-hoc comparisons, which will be corrected for multiple comparisons using the Holm-Bonferonni adjustment.

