#### 4. PROGRAMME AND METHODOLOGY

#### 4.1. Study Design

This research will involve a randomised, double-blind, crossover study that will assess the acute postprandial metabolic responses to three different test drinks. All three test drinks will be comprised of a high-fat milkshake with the addition of either maltodextrin, sucrose or lactose. Individuals will be required to attend the laboratories for a preliminary visit, followed by the three laboratory trial days, with a washout period of 28±7 days.

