### Laboratory trial days

On the evening before trial days, a 5-mL blood sample will be taken (via venepuncture) for analysis of baseline H enrichment of the body water pool. Participants will then consume a standardised meal with 3 g·kg body water  of H2O for the assessment of fasting hepatic DNL. Participants will continue to consume H2O throughout trial days for the measurement of postprandial DNL.

On postprandial study days, participants will arrive at the laboratories in a rested, overnight fasted state, after 24-hours of diet and physical activity standardisation.

Body mass will first be recorded, and then a cannula will be inserted retrograde into a pre-heated dorsal hand vein for arterialised blood sampling, and baseline blood and expired breath samples will be taken for analysis of plasma metabolite and hormone concentrations, plasma tracer enrichments, and indirect calorimetry, respectively. Participants will then consume a high-fat test drink containing 50 g of fat, plus 100 g of either **lactose**, **sucrose or maltodextrin (Table 1)**. The test drink will also contain 200 mg [U-C]palmitate in order to trace the fate of the dietary fat. This quantity of lactose is roughly equivalent to 400 mL of milk and 400 g plain yoghurt, which is very high but not supraphysiological in light of typical UK intakes.

Table 1. Main laboratory trials and drink composition.

| Trial        | Carbohydrate type mixed with fat source (100 g)      | Fat Source
(50 g)                |
|--------------|--|-------------------------------------|
| Maltodextrin | Glucose polymer; a common sugar substitute (control) | 30 g palm oil and
20 g olive oil |
| Lactose      | Galactose-glucose disaccharide (intervention)        | 30 g palm oil and
20 g olive oil |
| Sucrose      | Fructose-glucose disaccharide (active comparator)    | 30 g palm oil and
20 g olive oil |

Low-calorie-sweetened chocolate flavouring will be added to all drinks.

Participants will be advised that dairy products are used in this study and people following a vegan diet may therefore choose not to participate.

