Blood samples will be drawn at 30, 60, 120, 180, 240, 300 and 360 min after ingestion of the test drink and will be centrifuged for plasma collection and determination of metabolite and insulin concentrations (**Figure 4**). A portion of plasma will undergo density gradient ultracentrifugation to obtain the VLDL-rich [Svedberg flotation rate ( $S_f$ ): 20-400] and chylomicron-rich ( $S_f$ : >400) fractions. Expired breath samples will be taken at 60, 120, 180, 240, 300 and 360 min after ingestion for indirect calorimetry (Douglas bag method) and [ $^{13}$ C] appearance in expired CO2 (by isotope ratio mass spectrometry).

[figure not shown]

Figure 4. Schematic of the trial days

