### 4.10. Sample Size

Based on our preliminary data, co-ingestion of galactose increased postprandial plasma triglyceride incremental area under the curve by a further  $46.51 \pm 0.28$  mmol·L x 300 min (mean  $\pm$  SD) above glucose. Using this effect size (d = 0.75), 24 participants would provide a >90% probability (power = 0.94) of detecting such an effect with an  $\alpha$ -level of 0.05 using a one-way, repeated-measures ANOVA and accounting for post-hoc comparisons of three factors by the principle of closed testing. Accordingly, 24 adults will be recruited. **Dropouts will be replaced in a rolling fashion to ensure a complete sample size of 24. Based on our previous experience of similar studies, we expect a dropout rate of ~20% and thus anticipate recruitment of ~28 people to achieve this target.** 

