#### Primary analyses

Summary statistics (e.g. iAUC, AUC, peak concentrations) will be analysed by one-way ANOVA. Time-course data will be assessed by a two-way (time x treatment) ANOVA. Paired t-tests will be used for post-hoc comparisons, which will be corrected for multiple comparisons using the Holm-Bonferonni adjustment.

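### Repeated-measures ANOVA of the time courses needs all 24 samples from a participant, and the plan does not cover a single lost sample

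*Combined protocol and SAP*

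**What the plan says.** Section 4.11 handles time courses in three places.

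- Whole sample (Primary analyses): "Time-course data will be assessed by a two-way (time x treatment) ANOVA", followed by "Paired t-tests will be used for post-hoc comparisons".
- Men only and women only (Secondary analyses): "Time-course data will be assessed by a two-way (time x treatment) repeated measures ANOVA".
- Sex interaction (Secondary analyses): "Time-course data will be analysed by three-way (sex x treatment x time) mixed-model ANOVA".

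The sampling scheme is in sections 4.1 and 4.8. After a preliminary visit the design is "followed by the three laboratory trial days". On each trial day "baseline blood and expired breath samples will be taken", and then "Blood samples will be drawn at 30, 60, 120, 180, 240, 300 and 360 min after ingestion of the test drink".

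The only provision for incomplete data is in section 4.10: "Dropouts will be replaced in a rolling fashion to ensure a complete sample size of 24". Nothing states what happens when a participant attends all three visits but one sample is missed or cannot be assayed. There is no imputation or interpolation rule, no complete-case rule, and no model stated to accommodate incomplete data.

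**The concern.** Classical repeated-measures ANOVA works on a full participant-by-drink-by-time table. If one cell is empty, the usual default drops the participant, including the other 23 samples. Replacing dropouts does not help, because the person concerned has not dropped out.

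Two things are at stake. First, the number analysed can fall below 24, and by different amounts for different analytes, so the time courses would rest on different sets of people. Second, if samples are more often lost at visits that a participant tolerated badly, those excluded are not a random subset and the drink comparison could be biased. The alternative is a decision made after the data are seen, which a plan should avoid.

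**Working it through.** **Inputs.** Baseline plus seven later draws gives 8 samples per visit (section 4.8). Three visits (section 4.1) give 8 × 3 = 24 samples per participant per analyte. With 24 participants (section 4.10) that is 24 × 24 = 576 samples per analyte. The missing rate q is assumed, since the documents give none.

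**The plan's own figure.** Section 4.10 states power of 0.94 for d = 0.75 with 24 participants. A two-sided paired t-test at 0.05 gives 0.940, so the figure reproduces. It concerns the iAUC effect, and the documents give no corresponding figure for a time-course test or for missing samples. It is not used below.

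**Independent misses.** P(complete) = (1 − q)^24.

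| q (assumed) | P(complete) | Incomplete, of 24 | Incomplete, of 12 (one sex) |
|---|---|---|---|
| 0.5% | 0.887 | 2.7 | 1.4 |
| 1% | 0.786 | 5.1 | 2.6 |
| 2% | 0.616 | 9.2 | 4.6 |

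At 1% only 576 × 0.01 = 5.8 samples are expected to be missing. Losing 5.1 people to 5.8 samples is therefore close to the worst that this rate can do.

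**Misses in runs within a visit.** Suppose the same 1% comes in runs of m samples. The chance of a run at a visit is r = 0.01 × 8/m, and the expected number of incomplete participants is 24 × [1 − (1 − r)^3].

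- m = 2: r = 0.04, 2.8 participants
- m = 4: r = 0.02, 1.4 participants
- m = 8 (a whole visit): r = 0.01, 0.7 participants

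**Complete-data requirement.** A standard repeated-measures ANOVA routine, given simulated data of this shape, ran on the full table and refused it as unbalanced once one cell was removed.

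**Which mixed model can replace it.** Repeated-measures ANOVA tests drink against participant-by-drink variation, with 23 × 2 = 46 df. A model with only a participant random effect pools that with the participant-by-time (23 × 7 = 161 df) and three-way (23 × 14 = 322 df) variation, giving 529 df on complete data. Assume a residual SD of 1 and a visit SD of 0.5:

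- expected participant-by-drink mean square: 8 × 0.25 + 1 = 3.0; the others: 1.0
- pooled: (46 × 3.0 + 483 × 1.0)/529 = 1.174
- inflation of F for drink when there is no drink effect: 3.0/1.174 = 2.556
- 5% critical value of F(2, 529): 3.013; P(F > 3.013/2.556 = 1.179) = 31%

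Simulation with no true drink effect gave false-positive rates of 31% in this case, 32% with AR(1) correlation of 0.5 within visits, and 50% with AR(1) of 0.7. Repeated-measures ANOVA stayed at about 5% throughout. The correlation values are assumptions, but some correlation between serial plasma samples from one visit is to be expected.

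**The case against.** The strongest objection is that little depends on these tests. The primary outcome is triglyceride iAUC, the secondary outcomes are de novo lipogenesis and dietary fat oxidation, and the tertiary list consists of iAUCs and those same two measures. No named outcome is a time course, and section 4.11 analyses summary statistics separately. This stands: the time-course tests are supportive.

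A second objection is that exclusion is a default of the method, not a rule in the plan. The explicit repeated-measures wording governs only the two subgroups of 12. The term used for the sex interaction could mean a mixed-design ANOVA, with the same loss, or a linear mixed model, which would avoid it. This also stands. A reader might infer that the plan prescribes deletion of incomplete participants; it does not. It names a method that needs complete data and leaves the rest unsaid.

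Third, a participant who misses a whole visit would probably count as a dropout and be replaced. That reduces the gain from a mixed model for summary measures. It does not cover someone who attends but has no usable summary value for one visit.

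What survives is that the crossover design and paired post-hoc tests leave repeated measures as the only sensible reading for the whole sample, and that replacement does not reach single lost samples.

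**Conclusion.** The point holds for the supportive time-course tests. At an assumed 1% missing rate the expected loss is about 5 of 24 participants if misses are independent, and about 1 to 3 if they fall in runs within a visit. The rate, the pattern and the default exclusion are assumptions.

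Two stronger readings are not supported. One is that 1% missing samples would simply cost 5 participants: that figure needs independence, whereas a failed cannula would tend to produce runs. The other is that the stated power of 0.94 falls in step with the number of complete participants. That power rests on the iAUC effect size; it says nothing about a drink-by-time test, and losing someone from a time-course test does not remove them from the iAUC test. No power loss is claimed here.

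The change is still worth making. At 1% missing, a model on all available samples keeps all 24 participants and loses only about 6 of 576 samples.

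**What to change.** In section 4.11, under both Primary and Secondary analyses, replace the time-course ANOVAs with a linear mixed model fitted by REML to all available samples, with Kenward-Roger degrees of freedom:

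- fixed effects for drink, time and drink × time, plus the sex terms where planned;
- random effects for participant and for participant-by-drink (visit);
- a serial covariance within visits, such as AR(1), or a spatial-power structure because the sampling times are unequally spaced.

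A participant random effect alone must not be used for the time courses, for the reason shown in the working.

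For summary measures (iAUC, AUC, peak), use a mixed model with drink as a fixed effect and a participant random effect. With one value per visit this gives essentially the repeated-measures ANOVA result when data are complete, and it keeps a participant who lacks one visit's value. The plan should also say how iAUC is computed when a time point is missing, which it does not do now.

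The cost is revised wording, a covariance structure to pre-specify and slightly more analysis work. No new data are needed.

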### 4.12. Storage and Management of Data

Blood samples will be partially processed on the day of collection before freezing in preparation for analysis. Throughout this period and during the subsequent analysis, blood and breath samples will be kept in a locked laboratory and will be inaccessible to anyone outside of the research team. Samples will be coded and identified only using anonymized sample identifier numbers. After analysis, samples will be stored until the work has been published. We will ask participants to consent to their samples being used in any other ethically approved project during the lifetime of the current project.

Some analyses will be required to be performed at other sites (e.g. University of Oxford for Mass Spectrometry). These samples will be coded and identified only using anonymized sample identifier numbers for shipment.

If a participant wishes to withdraw from the study, they will be permitted to do so, however their samples will only be destroyed by specific request of the participant. Withdrawing participants will be reminded of this at the point of withdrawal, and should they not wish that their samples not be analysed or further stored, said samples will be destroyed immediately.

Any results published from this study will be anonymous and include no identifiable information. An Excel data sheet maintained on a University computer will be used to record participant information and results. The computer will be password protected to ensure only the designated researchers can access the data.

Whilst all measurements included in the protocol provide insight into physiology and health, of those that have recognised clinical significance and established normal ranges, only bone mineral density from DEXA can be provided in a clinically meaningful timeframe. As such, should a participant's data for this measure fall outside clinically normal ranges, we will inform the participant's GP directly by way of a letter, provided the participant has consented for us to do so.

# 4.13. Expenses and Benefits

Reasonable travel expenses for visits to the University will be reimbursed on production of receipts or via claims for mileage. Participants will also be offered a voucher (e.g. Amazon/Love2shop gift vouchers) with a value of £150 upon completion of the study. Participants will be provided with an information pack containing their results for relevant outcomes along with reference ranges (e.g., physical activity level, diet, body composition, blood tests).

#### 5. DISADVANTAGES/RISK AND DISCOMFORT

Participants will be asked to give up their time for repeated visits to undertake various tests. For some people this may be seen as an inconvenience. Blood samples will be collected using an intravenous catheter, which might cause minor discomfort during the procedure and may result in minor bruising. More serious complications are the very small risk of infection. However, the occurrence of such events is very rare and risks are further minimised by our strict adherence to best practice and standard operating procedures.

We will measure fat mass, fat-free mass, and bone mineral density, using dual-energy x-ray absorptiometry (DXA). DXA scans are non-invasive radiologic projection scans that use very low radiation, often compared to the exposure to background radiation experienced on daily basis in the UK. For the sake of the present study, this equates to less than one day of background radiation (and a tiny fraction of the amount of radiation experienced during a typical X-ray). These techniques are routinely used in hospitals and with elite athletes but nonetheless they do represent some exposure to a small amount of radiation.

We will utilise stable isotope tracers to determine key aspects of postprandial metabolism. These stable isotopes are non-radioactive and therefore pose no long-term risk to the health of the participants. On the evening prior to the study day, the participants will consume a loading dose of  $^2\text{H}_2\text{O}$  (heavy water). The loading dose of  $^2\text{H}_2\text{O}$  given is the amount to achieve a plasma water enrichment of 0.3%. This will be split into two equal doses with a ~2 h gap between consumption. This will decrease the likelihood of the participant feeling "dizzy" which can occur within ~1 hour

after consuming the water. Individuals prone to travel sickness appear to be more likely to get "dizziness" after consumption of water, but this dizzy feeling is transient and not harmful.

The above will be explained to the potential participant verbally and in the participant information sheet to ensure that they are fully informed before giving consent.

